5.1.1.3 Radiation Therapy Adverse Events

Grade 3-4 (CTCAE, v. 4.0) therapy-induced mucositis and/or dysphagia, which are enhanced by cisplatin, are expected to develop in about two thirds of patients. Nutritional evaluation prior to the initiation of therapy for a prophylactic gastrostomy (PEG) tube placement is highly recommended. Placement of a feeding tube should be recorded, as should use of a feeding tube during and after treatment (e.g. greater than or less than 50% of nutrition by tube). Other common radiation adverse events include: fatigue, weight loss, regional alopecia, xerostomia, hoarseness, transient ear discomfort, dysgeusia, and skin erythema and desquamation within the treatment fields. Less common long-term treatment adverse events include: hypothyroidism, loss of hearing, chronic swallowing dysfunction requiring permanent feeding tube, and cervical fibrosis. Much less common radiation adverse events include: mandibular osteoradionecrosis, and cervical myelopathy ($< 1\%$ with restriction of spinal cord dose to ≤ 45 Gy).

5.1.1.4 R.T. Quality Assurance Reviews

RTOG uses several approaches to ensure H&N IMRT quality assurance (QA) including H&N anatomic atlases, site and machine certification of H&N IMRT, and individual case reviews. The department QA committee will perform RT Quality Assurance Reviews for this trial.

Technical Factors, Localization, Simulation, and ImmobilizationPatients must have an immobilization device (e.g. Aquaplast mask) made prior to treatment planning CT scan. The treatment planning CT scan should be performed with IV contrast so that the major vessels of the neck are easily visualized. The treatment planning CT scan must be performed with the immobilization device and in the treatment position. Slice thickness should be 0.3 cm.

Treatment Planning/Target Volume: Planning Target Volumes (PTVs): In general, the PTV should not go outside of the skin surface; if it does exceed the skin surface, the application of bolus material over this portion of the PTV may be considered if it is judged clinically that the skin is at risk but is generally not recommended. In general, the CTV-to-PTV expansion (without IGRT) should not exceed 10 mm. In general, the CTV-to-PTV expansion (with IGRT) should not exceed 5 mm.

Definition of Normal Tissues/Organs at Risk (OARs): NOTE: Only the parts of the normal tissues/organs at risk outside the PTVs will be considered for dose optimization purposes.

Spinal Cord: The cord begins at the cranial-cervical junction (i.e. the top of the C1 vertebral body). Superior to this is brainstem and inferior to this is cord. The inferior border of the spinal cord is at

approximately T3-4 (i.e., just below the lowest slice level that has PTV on it). The spinal cord shall be defined based on the treatment planning CT scan. In addition, however, a Planning Risk Volume (PRV) spinal cord shall be defined. The PRV_{cord} = cord + 5 mm in each dimension. This is irrespective of whether or not IGRT is used.

Brainstem: The inferior most portion of the brainstem is at the cranial-cervical junction where it meets the spinal cord. For the purposes of this study, the superior most portion of the brainstem is approximately at the level of the top of the posterior clinoid. The brainstem shall be defined based on the treatment planning CT scan. In addition, however, a Planning Risk Volume (PRV) brainstem shall be defined. The PRV_{brainstem} = brainstem + 3 mm in each dimension.

Lips and Oral Cavity: These should be contoured as 2 separate structures as the goal is to keep the lip dose much lower than the oral cavity dose. The oral cavity will be defined as a composite structure consisting of the anterior $\frac{1}{2}$ to $\frac{2}{3}$ of the oral tongue/floor of mouth, buccal mucosa, and palate.

Parotid Glands: Parotid glands will be defined based on the treatment planning CT scan.

Cervical Esophagus: This will be defined as a tubular structure that starts at the bottom of oropharynx and extends to the thoracic inlet.

Glottic/Supraglottic Larynx (GSL): This will be defined as a “triangular prism shaped” volume that begins just inferior to the hyoid bone and extends to the cricoid cartilage inferiorly and extends from the anterior commissure to include the arytenoids. This includes the infrahyoid but not suprathyoid epiglottis.

Mandible: This includes the entire bony structure of the mandible from TMJ through the symphysis.

Unspecified Tissue Outside the Targets: This will be defined as tissue located between the skull base and thoracic inlet that is not included in either the target volumes or the normal tissues described above.

5.1.1.5 IMRT Dose Prescription to PTVs

The goal is for 95% of the planned PTV to receive ≥ 2 Gy with a minimum dose (cold spot) It is recognized that portions of the PTV close to the skin may receive significantly less. This is acceptable as long as cold spots within PTV1 do not exist at a depth deeper than 8 mm beneath the skin

For planning prioritization and priorities in dose coverage, in the final plan, PTV1 will be the highest priority target structure. PTV2 and PTV3, if applicable, will be ranked in the IMRT planning as lower priority than PTV1m although usually at a higher priority than normal structures other than spinal cord and brain stem.

Doses to Normal Structures

Spinal Cord: The PRV_{cord} should not exceed ≤ 50 Gy to any volume in excess of 0.03 cc (approximately 3 mm x 3 mm x 3 mm).

Brainstem: The PRV brainstem (as defined in Section 6.4.2.2) should not exceed 52 Gy to any volume in excess of 0.03 cc (approximately 3 mm x 3 mm x 3 mm).

Lips: Reduce the dose as much as possible. The mean dose should be < 20 Gy.

Oral Cavity: Reduce the dose as much as possible. The mean dose should be < 30 Gy for the non-

involved oral cavity. Efforts should also be made to avoid hot spots (> 60 Gy) within the non-involved oral cavity.

Parotid Glands: In most cases, it will be easier to spare one parotid than the other. The treatment planning goal will be for this individual parotid gland to receive a mean dose of < 26 Gy.

Contralateral submandibular gland: If contralateral level I is not a target, aim to reduce mean contralateral submandibular gland to < 39 Gy.

Mandible: Reduce the dose as much as possible. Hot spots within the mandible should be avoided. It is recommended that maximum dose within the mandible be < 66 Gy.

Unspecified Tissue Outside the Targets: No more than 1cc of unspecified tissue outside the targets can receive 74 Gy or more.

Prioritization for IMRT Planning

1. Spinal Cord
2. Brainstem
3. PTV1
4. PTV2 (if applicable)
5. PTV3 (if applicable)
6. a. Oropharynx b. Parotid gland contralateral to primary tumor site
7. a. GSL b. Esophagus
8. a. Lips b. Oral Cavity
9. a. Parotid gland ipsilateral to primary tumor site b. Mandible
10. Unspecified tissue outside the targets

5.1.2 Drug therapy

All systemic therapies are considered standard of care, and toxicities and dose modifications will be made by the treating physician based on institutional standards. Drugs are commercially available and are not considered investigational.

Patients Receiving Cisplatin or Cetuximab with Concurrent Radiation Therapy (RT)

Patients who receive cisplatin, will receive 100 mg/m², administered intravenously every three weeks (with a three day window) as per institutional standard. Patients who receive cetuximab will receive a loading dose of 400 mg/m² given at least 5 days prior to radiation initiation and 250 mg/m² given weekly during radiation. Chemotherapy can be given either before or after the radiation therapy fraction that is given on the same day. If radiation is held for more than 2 days (for any reason), cisplatin may be held as well until radiation resumes. High dose cisplatin is a highly emetogenic regimen with significant incidence of delayed nausea and vomiting whereas cetuximab is less than that at Gen.. Institutional guidelines for anti-emetic regimens should be followed per physician preference and institutional guidelines. Supportive care guidelines will vary by drug type but are standardized at the Markey Cancer Center via standardized chemotherapy order sets and electronic medical record order entry for all patients.

5.1.3 Beetroot Administration

Study Supplements:

Subjects will be given 10 grams of concentrated organic beetroot crystals to mix with 120ml of water (BEETELITETM). Beetelite study supplement readily dissolve in water and may be given via gastrostomy tube or orally.

Daily Supplement Administration:

Subjects will begin daily supplementation following baseline measures (1-2 weeks before 7-week IMRT and for a minimum of 4 days) and will continue supplementation 4-6 weeks after treatment. Patients will be taught to self-administer their assigned study beverage by mouth and via PEG (as needed) by study staff during the baseline measurement period for the entirety of the trial. Patients requiring enteral support will be taught how to self-administer their assigned study beverage by a CRA or CRN. Compliance will be monitored by verbal assessment at clinic visits and by collection of written logs. Written instructions (Appendices E and F) for proper mixing of study beverage powders with water will be provided to both study volunteers and MCC staff involved in supplement administration and supervision. MCC staff will supervise the initial self-administration to ensure uniformity of ingestion. Subjects will be required to record the supplement intake in a dietary log which will be reviewed frequently at clinic visits.

Beetroot will be self-administered daily (M-F) at the same time each day during the afternoon hours (12pm-5pm) and if possible, should be dosed after radiation to promote a consistent administration/habit. IDS will provide pre-measured 10g portions of the supplement powder each week during the IMRT period. The patient will mix and administer, and will record that they took the product daily in the compliance log that will be brought back and assessed at clinic. If at any point during the 7-week IMRT treatment the patient is unable to self-administer, the patient's family or study personnel who are recognized as clinical providers (such as a CRN) will mix the water and powder and will aid in supplement administration if the patient wishes to continue with the study. Subjects will then be discharged with beetroot for daily dosage (M-F) throughout the post IMRT follow-up period. Standard PEG tube care guidelines will be followed and the tube will be flushed with 30 to 50mL of water before and after every supplement dose. For patients requiring supplement administration assistance at IMRT discharge, a family member or caregiver of the patient will be identified and taught to provide assistance during the MP-EP follow-up period. An additional copy of the written mixing/administration instructions will be provided at this time and study staff will offer additional instructional assistance as needed.

Subjects who vomit the beetroot within the first 15 minutes after administration may repeat the administration once that same day. If vomiting occurs greater than 15 minutes after administration, the dose should not be repeated. Vomiting will be closely monitored and additional supplement packets will be provided at discharge in case of vomiting.

Study volunteers will be asked to retain all used and unused study packaging on a weekly basis to turn in to study staff at the end of the week. Study packaging will be compared to the patient generated compliance log to document weekly compliance data. Subjects who are deemed "non-compliant" with the beetroot protocol (less than 3 consumed supplements during any 1 week period between baseline and midpoint measures) will be excluded in the per protocol analysis. Compliance to beet root consumption between midpoint and endpoint measure will be encouraged with weekly phone calls by nutrition graduate students supervised by [name]. [name] will oversee all aspects of the supplementation protocol. The Investigational Drug Service (IDS) at the University of Kentucky will assist with storage, supply management, quality control, and transfer of all beet root.

Bulleted supplementation administration guidelines for each study period are provided below: Baseline and prior to IMRT enrollment (supplement initiation period):

- Following randomization, participants will be taught to self-administer their supplement by study personnel.

- The CRA or nutrition student will then distribute the supplement needed for the 1-2 weeks prior to IMRT to the participant.
- The supplement powder will be packaged in 10g portions by the IDS. Packaging will only be identified by the letter “A” or “B” and only IDS staff will be unmasked to supplement assignment.
- Participants will begin daily, single dose supplementation (M-F during the afternoon hours) on the first day of receiving their supplement from study personnel.
- Participants will be taught to mix their assigned powder with 120mL of water and self-administer within 30 minutes of mixing.
- Compliance during this time period will be encouraged by phone calls, a supplement “count,” and with a patient generated supplement log sheet.

7-8 week IMRT treatment period (daily supplement observation period):

- Participants will be asked to continue daily (M-F) self-administration of the supplement. The pre-measured supplement powder will be provided to the participant on a weekly basis and patients will be asked to consume the supplement during the afternoon hours (M-F).
- At the beginning of treatment and throughout the IMRT period, study personnel will assess the need to provide additional education on proper self-administration of the study supplement (ex. Transitioning from PO feeding to enteral feeds).
- CRNs serving as study personnel may offer observation or administration assistance if patient requests this and may document supplement compliance.
- Patients will be instructed to make up any missed doses by taking up to 1 additional dose per day on the weekend days. Patients will receive 5 doses per week (for M-F) and will be instructed to never exceed 1 dose per day.

4-6 weeks post-IMRT (discharge period):

- After completion of IMRT the participant will be instructed to continue daily (M-F) self-administration (PO or PEG) until completion of endpoint measures.
- For patients requiring supplement administration assistance at discharge, a family member or caregiver will be identified and taught to provide assistance.
- On the day of discharge and during scheduled follow-up visits, the CRA will distribute the pre-measured supplement packets needed for daily administration.
- Participants will continue to follow the supplement mixing protocol and be reminded to consume their assigned supplement within 30-minutes of mixing.
- Supplement compliance will continue to be encouraged by weekly phone calls by study personnel and compliance logs/supplement counts will occur at least twice per month.

Supplementation on Testing Days

On testing days, The BEETELITE™ solution (beet root) will be administered on-campus 20-45 minutes before subjects undergo the baseline, midpoint (following IMRT), and endpoint (4-6 weeks following midpoint) strength/endurance measures. Prior to testing, subjects will not have to refrain from standard oral care, using antibacterial mouth wash, or chewing gum 48 hours before testing sessions because the BEETELITE™ product does not rely on salivation/oral bacteria to convert dietary nitrate to nitrite (23). Previous studies have administered up to 500mL of beet root per day with nitrate concentrations of 5.5 mMol (24), 6.2mMol (7, 25), 5.2mMol (26), and 5.1mMol (27). Plasma nitrite (NO_2^-) levels in these aforementioned studies also increased following dietary nitrate supplementation.

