5.1.5 Testing procedures at Baseline, Midpoint and Endpoint of therapy

All testing procedures, unless otherwise indicated, will be performed at the Markey Cancer Center (MCC) and the Center for Clinical and Translational Science (CCTS). Testing will occur at Baseline (Pre-IMRT), Midpoint (week number 7-8 following IMRT initiation), and Endpoint (4-6 weeks following Midpoint testing). A range of testing times at midpoint and endpoint are provided for subject convenience and flexibility with medical follow-up appointments. Primary outcome measure: 1) IMRT treatment compliance- No delays in treatment of radiation and/or chemotherapy (Cycles: Namely 35 fraction of daily radiation therapy (Monday-Friday) with 100 mg/m² cisplatin on days 1, 21, & 43. Total duration of therapy = 50 days). Treatment compliance will be defined as completion of all radiotherapy or completion of all radiotherapy plus prescribed chemotherapy without dose reduction or delay of radiation therapy that would extend treatment beyond 50 days.; Secondary outcome measures: 1) muscle strength/function, 2) serum/salivary nitrate/nitrite, 3) preservation of fat-free mass (CT/DXA), 4) mucositis symptoms, 5) nutrition assessment, 6) quality of life g. Details of each test are provided in section 9.0.

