5.3 Duration of Therapy

Subjects will be removed from study if one of the following occurs:

- Subjects who do not complete at least 50% of the planned medical therapy
- Intercurrent illness that prevents further administration of medical treatment,
- Unacceptable adverse event(s),
- Patient decides to withdraw from the study, or
- General or specific changes in the patient's condition render the patient unacceptable for further treatment in the judgment of the investigator.

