13.4.2 Evaluation of Outcomes

All patients included in the study will be assessed for treatment compliance, even if there are major protocol treatment deviations or if they are ineligible. All of the patients who met the eligibility criteria (with the possible exception of those who received no study medication) will be included in the intent to treat analysis for the primary completion endpoint as well as all secondary outcomes.

Due to concerns of potential non-compliance of taking all beet supplements over the course of primary treatment, a per protocol analysis will also be performed for all patients that consume at least 3 servings of the required beet supplements per week. Percentage of beet supplements taken will also be reported as part of this subgroup analysis.

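### The per-protocol set is selected on supplement intake during the weeks that decide treatment compliance, so its compliance rate is expected to be too high; the all-patient estimate is not affected

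*Combined protocol and SAP*

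**What the plan says.** **The filter.** Section 5.1.3 excludes a patient on the strength of one low week ("less than 3 consumed supplements during any 1 week period between baseline and midpoint measures) will be excluded in the per protocol analysis"). Section 13.4.2 says "a per protocol analysis will also be performed for all patients that consume at least 3 servings of the required beet supplements per week", without naming a window or saying whether a single low week is enough.

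**The window.** It opens before radiotherapy: "Subjects will begin daily supplementation following baseline measures (1-2 weeks before 7-week IMRT and for a minimum of 4 days"). It closes at the midpoint visit: "Midpoint (week number 7-8 following IMRT initiation").

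**The outcome.** Section 5.1.5 states: "Treatment compliance will be defined as completion of all radiotherapy or completion of all radiotherapy plus prescribed chemotherapy without dose reduction", and adds the condition that there be no "delay of radiation therapy that would extend treatment beyond 50 days".

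**Links between the two.** Section 5.3 removes from study "Subjects who do not complete at least 50% of the planned medical therapy", as well as patients with unacceptable adverse events or an illness that prevents further treatment. Section 6 holds the supplement for grade 3 or 4 events at least possibly related to beetroot and then moves to three doses a week. Section 5.1.1.3 expects grade 3-4 mucositis and/or dysphagia in about two thirds of patients.

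**Other analyses.** Section 13.4.2 assesses every included patient for treatment compliance and plans an intent-to-treat analysis of the primary and secondary outcomes. The per-protocol analysis is additional. On intake it says: "Percentage of beet supplements taken will also be reported as part of this subgroup analysis". Section 1.2 separately defines feasibility, for each patient, as the proportion of days on which the supplement was taken during treatment.

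**The concern.** A per-protocol set is informative about an outcome only if membership does not depend on that outcome or on its causes. Here it probably does. Severe mucositis, vomiting, an intercurrent illness or removal from study can each cause a week with fewer than three supplements, and each can also cause the delay, dose reduction or early stop that counts as treatment failure. Failures would then leave the set more often than completers, and the rate among those who remain would rise even if beetroot had no effect.

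At stake is how the per-protocol rate is read. Set beside the 52.1% historical rate, or beside the observational cohort, to which no intake filter applies, it could look like a benefit of taking the supplement when it may only show that patients who tolerate treatment can also take the drink. Section 13.4.2 gives no warning of this and does not say which rate should inform the larger study.

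**Working it through.** **1. The plan's own precision figures.** Section 13.3 specifies exact 90% binomial intervals. The maximum half-widths are:

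| n | Recomputed | Stated in 13.2 |
|---|---|---|
| 10 | 27.76% | 27.75% |
| 15 | 22.81% | 22.85% |
| 25 | 17.67% | 17.7% |

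These reproduce, so 17.7 points is a fair yardstick for the combined rate.

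**2. Overlap of the windows.** Intake is judged from 1-2 weeks before radiotherapy to week 7-8 after its start. The outcome is decided within about 50 days of the start, and 50/7 = 7.1 weeks. Only the pre-radiotherapy weeks lie clearly outside, so the overlap is near-complete.

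**3. Bias formula.** Let p be the true compliance rate, ec the share of completers excluded and en the share of failures excluded. Then

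per-protocol rate = p(1 − ec) / [p(1 − ec) + (1 − p)(1 − en)].

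It equals p when ec = en and exceeds p when en > ec. The documents give neither ec nor en, so both are assumptions. From 13.2, p = 0.6 × 70% + 0.4 × 52.1% = 62.84%. With ec = 5%:

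| en | Calculation at p = 62.84% | Rate | Bias (points) |
|---|---|---|---|
| 5% | 0.597/(0.597 + 0.353) | 62.8% | 0 |
| 20% | 0.597/(0.597 + 0.297) | 66.8% | +3.9 |
| 30% | 0.597/(0.597 + 0.260) | 69.7% | +6.8 |
| 50% | 0.597/(0.597 + 0.186) | 76.3% | +13.4 |

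For en of 20 to 50%, p = 52.1% gives +4.3 to +15.3 points and p = 70% gives +3.5 to +11.6. With ec = 20% and p = 62.84%, en of 30 to 50% gives +3.1 to +10.2.

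**4. In patient counts.** If 15 of 25 comply, the rate is 60.0% (exact 90% interval 41.7 to 76.4). Excluding 5 of the 10 failures and no completer gives 15/20 = 75.0% (54.4 to 89.6), with no patient's outcome changed.

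**5. Would cutting the window at the first treatment event be enough?** Assume independent doses with a common probability of being taken, five scheduled doses a week, 8 weeks at risk for completers, 3 for failures, and true compliance of 64% (16 of 25).

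- *Any-week rule, dose probability 0.8.* The chance of fewer than 3 of 5 doses in a week is 5.79%. Completers excluded: 1 − 0.9421^8 = 38%. Failures excluded: 1 − 0.9421^3 = 16%. Expected rate: 9.93/(9.93 + 7.52) = 56.9%, about 7 points too low.
- *Any-week rule, dose probability 0.9.* The weekly chance is 0.86%, exclusions are 6.6% and 2.5%, and the rate is 14.94/(14.94 + 8.77) = 63.0%, 1 point too low.
- *At least 60% of scheduled doses over the same periods* (24 of 40 for completers, 9 of 15 for failures). At 0.8, 99.9% and 98.2% are kept and the rate is 64.4%. At 0.9, nearly all are kept and the rate is 64.0%.

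Truncating the any-week rule therefore reverses the bias, while a share-of-doses rule nearly removes it under these assumptions.

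**The case against.** The strongest reply is that little depends on this rate. The primary analysis covers all included patients, the per-protocol analysis is an addition that 13.4.2 itself calls a subgroup analysis, and the interim look uses the first 13 beetroot patients enrolled, without an intake filter. Section 13.2 ties precision and the pilot's purpose to all 25 beetroot patients. All of this stands, and it limits the point to interpretation of a secondary rate.

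The plan also weakens the link between toxicity and missed doses through tube administration, assisted dosing, a repeat dose after early vomiting, weekend make-up doses and a threshold of three in five. That lowers en but does not cover holds, removal or patients who stop.

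Four stronger readings are tempting and not supported:

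- *The trial's main result is biased.* It is not; no intake filter touches it.
- *The gain is 9 to 20 points.* Taking 16/25 to 16/22 = 72.7% or 16/19 = 84.2% requires losing 3 to 6 of 9 failures and no completer. Losing 4 of 16 completers and 3 of 9 failures gives 12/18 = 66.7%, only +2.7.
- *A patient removed early is automatically excluded.* Neither section says whether weeks after removal count. That is a gap to close, not a settled rule.
- *Reported intake is at least 60% by construction, so feasibility is lost.* The floor of 3/5 holds only up to midpoint. A patient taking 3 of 5 doses for 8 weeks and none for the next 4-6 passes the filter at 24/60 to 24/70, or 40 to 34%, over the full course. Sections 1.2, 13.1 and 13.4.2 already plan feasibility without selection.

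**Conclusion.** The point holds for the per-protocol compliance rate only. Selection on intake in the weeks that decide the outcome is written into 5.1.3, and sections 5.3 and 6 give reasons to expect failures to be excluded more often than completers, so the expected direction is upward. The window overlap is certain. The size is not known: about +4 to +15 points if 5% of completers and 20 to 50% of failures are excluded, and zero if the two shares are equal. The upper part of that range approaches the 17.7-point margin, and a larger sample would not reduce it. Sections 5.1.3 and 13.4.2 also give two different rules, which could produce different sets from the same data. The correction is worth making because it is cheap, not because the primary estimate is at risk.

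**What to change.** 1. **Section 13.4.2, status of the rates.** State that the all-patient rate is the only basis for conclusions and for planning the larger study. Print the per-protocol rate beside it, labelled descriptive, with the number of patients excluded, the reason for each exclusion and their treatment-compliance outcomes.
2. **Sections 5.1.3 and 13.4.2, one definition.** Replace the two rules with a single one that does not count weeks after treatment stop or removal, or weeks of a protocol-directed hold, as supplement non-compliance. Define it by the share of scheduled doses taken up to that date, for example at least 60%, which matches the present three in five. Do not simply truncate the any-week rule: failures would have fewer weeks at risk of exclusion and the rate would be biased downward.
3. **Section 13.4.2, intake.** Report the percentage of supplements taken for all beetroot patients, in line with the feasibility definition in 1.2, with the subgroup figure only as an addition.

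The cost is wording, one derived date per patient and one extra table. The small downside is that early failures enter the per-protocol set with little exposure. Shared causes that act before the cut-off date also remain, which is why the descriptive label is still needed.
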